4. TRIAL INTERVENTIONS

Each woman randomized into the WAVE trial will receive either ether active or placebo hormone replacement therapy (HRT) and either active or placebo antioxidant supplement.

4.1 SELECTION OF HORMONE REPLACEMENT THERAPY

The selection of the HRT for the WAVE trial was guided by the following considerations: the medications selected should be well studied; approved for use in the United States; the safety concerns and side effects should be well known and it must be possible to address them as either an exclusion criteria or through careful post-randomization monitoring. There are currently limited data available comparing the cardiovascular effects of the various commercially available estrogen preparations. In the United States, the most commonly prescribed estrogen preparation is conjugated equine estrogen (CEE). CEE is currently being studied in the Women's Health Initiative (WHI), the Heart and Estrogen Progestin Replacement Study (HERS) and Estrogen Replacement and Atherosclerosis (ERA) trials. Using this preparation in the WAVE trial will allow for comparisons among some of the current major cardiovascular trials in women using HRT. Therefore the WAVE trial will use CEE (0.625 mg daily) as the estrogen component of its HRT.

Recent data in the Postmenopausal Estrogen/Progestin Interventions trial (PEPI) indicate that the use of unopposed estrogen in women with a uterus is associated with significant compliance problems and increased prevalence of side effects (152). However, in PEPI, the combination of CEE with a progestin significantly reduced the risk of endometrial hyperplasia. Therefore, in the WAVE trial women without a uterus will receive an unopposed CEE (Premarin), while women with a uterus will receive Prempro, a combination of a CEE and continuous progestin, 2.5 mg medroxyprogesterone acetate

(MPA). Premarin, Prempro and their respective placebos, will be supplied by Wyeth-Ayerst. Each will be provided as a single capsule containing either active or placebo medications.

Several considerations led to the selection of the progestin. Concern has been raised that the addition of a progestin may diminish the putative cardiovascular benefits of estrogen replacement therapy. Progestins alone tend to raise LDL and lower HDL cholesterol levels. In the PEPI trial, all hormone regimens lowered LDL cholesterol levels, but medroxyprogesterone acetate (MPA) significantly attenuated the estrogen related increase in HDL cholesterol levels. Oral micronized progesterone in doses of 1 and 2 mg appeared to have the least detrimental effect on plasma lipoprotein levels. However there is little safety information on the long-term use of continuous micronized progesterone. The Nurses Health Study data suggests that the addition of progestin does not appear to attenuate the cardioprotective effects of post menopausal estrogen use. The choice of MPA will also allow for it to be combined in a single capsule with the CEE selected. By reducing the number of daily capsules that each woman with a uterus will have to take, compliance in the HRT arm of the trial should be increased.

4.2 SELECTION OF ANTIOXIDANTS

A dose-ranging study to assess protection of LDL from oxidation suggested that the minimum dose of alpha tocopherol needed was 400 IU per day with further prolongation of the lag phase of LDL oxidation at 800 and 1200 IU (141). There was wide inter-individual variation at identical vitamin E doses. The correlations between plasma LDL, alpha-tocopherol and oxidation kinetics were approximately 0.5-0.6 for most parameters. A subgroup analysis from the Cholesterol Lowering Atherosclerosis Study relating angiographic progression of coronary lesions to in-trial vitamin E intake, suggested that intakes above 100 IU of vitamin E among the male study subjects were protective (142).

Vitamin C is a water-soluble essential vitamin with antioxidant properties and possible beneficial effects on coagulation and fibrinolytic factors (143). It spares vitamin E and may thus enhance the effects of vitamin E. Epidemiologic data are mixed, but some studies have reported a lower incidence of stroke (144) and a lower cardiovascular mortality with increased vitamin C intake (145, 146). The effect of Vitamin C on progression of coronary disease was not apparent in the study of Hodis (142).

Vitamin E is generally well tolerated, but prolongation of prothrombin time among vitamin K deficient patients has been documented and, in rare cases, it may result in clinical bleeding (147). A more recent study using 800 or 1200 IU in patients concurrently prescribed warfarin did not demonstrate any significant effects on coagulation parameters (148). Vitamin C also appears to be quite safe even at large doses (150). Although earlier studies suggested that high vitamin C intakes may predispose to nephrolithiasis by increasing oxalate concentration in the urine more recent studies suggest that the increased urine oxalate content is a measurement artifact (151). Consistent with this observation, an increase in renal stone formation was not apparent in the Health Professionals' Study at doses of vitamin C of 1500 mg and higher when compared to intakes of less than 250 mg (149).

Women will be randomized to an active anti-oxidant therapy consisting of Vitamins E and C or their matching placebos. The preparations will be provided as 400 IU capsules of vitamin E and 500 mg tablets of vitamin C, BID for a total daily dose of 800 IU vitamin E and 1000 mg vitamin C. The active and placebo vitamins will be supplied by BASF/Knoll.

5. MASKING

To promote uniform follow-up of all trial participants, all randomized women and clinical center personnel responsible for randomization and follow-up will, to the extent possible, remain masked to treatment assignments until the end of the trial. This will increase the probability that all women will receive similar concomitant treatments, testing and evaluation during the conduct of the trial. It is likely however that due to the occurrence of side effects, some women and/or clinical personnel will assume knowledge of one of their treatment assignments. Women will be instructed to not discuss gynecological issues with WAVE cardiology staff. Rather, each center will have a study gynecologist, or designated personnel to whom women can address concerns about side effects.

Each woman with a uterus will be asked to fill out a bleeding diary for the first six months following randomization. The diary will be returned to the gynecology staff. After review of the entries at the first six month visit, a decision by the OB/GYN physician will be made as to whether or not the diary may be discontinued.

Personnel at the central angiographic laboratory and the central biochemistry laboratory, will also be masked to treatment assignments. This will permit unbiased assessments of the trial's primary and secondary outcomes.

6. INFORMED CONSENT

Each Principal Investigator will be required to submit the WAVE protocol to their local IRB for approval. As part of this process, an appropriate informed consent form will be developed at each site. A copy of the IRB approval letter and a copy of the consent form approved by the local IRB will be forwarded to the NHLBI project office. No randomizations will be permitted prior to the receipt of these documents. The consent form will, at a minimum, meet the guidelines from the Code of Federal Regulations, part 46 – Protection of Human Subjects. A sample informed consent form is included in Appendix A. The SCC will send reminders for annual renewals of each center's IRB approval and will request that copies be sent to the NHLBI project office.

7. STUDY VISITS

7.1 SCREENING

It is anticipated that on average each of the five WAVE clinics will randomize 90 women. To accomplish this goal each coordinator will monitor the daily catheterization laboratory logs and other potential sources, to identify likely candidates for the trial. The coordinators will be free to design an identification program that is efficient for their local conditions. However, it is anticipated that the initial identification of potential WAVE participants will be by: reviewing logs of diagnostic catheterizations; pre- and post-intervention catheterizations; reviewing existing databases to identify women from other research programs. A goal of the WAVE trial is to have an appropriately ethnically diverse study cohort. To accomplish this, each site will develop a plan to recruit minority women. This will include educating cardiology fellows about the trial, recruiting nurse practitioners from clinics that serve minority populations, reviewing records from ongoing studies that are recruiting minority women, interacting with community leaders to provide information about the trial and development of recruitment and retention aids that are culturally sensitive. Prior to randomization, the clinics will submit their proposed screening procedures to the Study Coordinating Center (SCC), which will produce a summary of all the programs to be distributed to all five sites. Prior to randomizing any patient, a local investigator will contact the patient's physician. It is crucial to obtain the commitment and support of the patient's physician in assisting and maintaining compliance to the protocol for the duration of the trial.

The procedures to be followed and the data to be collected at the screening and follow-up visits are outlined below.

7.2 SCREENING VISIT

The study will be described to the potential participant and if she agrees to participate, an informed consent form should be reviewed and signed.

If creatinine and fasting triglycerides have been assessed within the past twelve months, no blood collection is necessary at this visit. If they are not available, the patient will be asked to fast for at least twelve hours prior to coming to clinic and a blood sample will be taken. This should be sent to the local laboratory for analysis of creatinine, triglycerides, FSH and INR, as necessary.

A general physical (including a mammogram, if none has been done in the last 12 months, a PAP smear and a pelvic examination) is to be completed. If a mammogram has been done within the past twelve months, the coordinator will obtain a medical release from the patient and obtain a copy of the results. For women participating in the Brachial Artery Reactivity Study (see appendix D) and the Effects of Hormone Replacement Therapy on Electrocardiographic and Scintigraphic Measures of Myocardial Ischemia Study (see appendix E) appropriate assessments will be performed. However, a woman who is otherwise eligible may refuse either or both of these studies and still be randomized into the WAVE trial.

Comment [TBC1]:

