3. THE STUDY COHORT

3.1 PATIENT ELIGIBILITY

The eligibility and exclusion criteria are as broad as possible to increase the generalizability of the results while maintaining patients' safety and the scientific integrity of the trial. There is no upper or lower age limit for participants, however, participants must meet all inclusion criteria and have none of the exclusion criteria. All potential participants with any single exclusion criteria will be excluded. However, such patients may be reconsidered for eligibility at a later time (for example, if a patient had an MI less than four weeks prior to randomization, they may be reconsidered at a later time). However, all of the trial's inclusion and exclusion criteria must be reevaluated when they are reconsidered.

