3.2 INCLUSION CRITERIA

To be eligible for randomization, women must:

1. Be postmenopausal by one of the following criteria:
 - a. Have had a bilateral oophorectomy at any age,
 - b. Be ≥ 55 years of age (or have an FSH ≥ 40 , if under age 55)
 - c. $<$ age 55 and FSH ≥ 40

Women under 45 years of age without a bilateral oophorectomy, or FSH ≥ 40 are excluded.

2. Have a WAVE protocol angiogram performed within four months of randomization, while hemodynamically stable, demonstrating at least one vessel segment with a 15-75 percent stenosis. The qualifying artery may not have been intervened (dilated, atherectomized or stented). If the angiogram was performed within 2 weeks of a myocardial infarction, the qualifying segment may not be the infarct segment.
3. Provide signed informed consent.

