3.3 EXCLUSION CRITERIA

1. Concurrent hormone replacement therapy (HRT) which will not be terminated. If on HRT for at least three months when screened, a washout period of 3 months is advisable. Women using estrogen vaginal cream are eligible if they use it no more than 25 percent of the time.
2. Concurrent vitamin supplements exceeding the RDA for vitamins C (> 60mg/day) and/or E (> 30 IU/day), which the patient is unwilling to stop. Women taking vitamins will be offered the alternative of stopping and taking Centrum Silver, provided by the WAVE trial.
3. History of breast cancer or mammogram suggestive of cancer without a subsequent negative biopsy.
4. History of endometrial carcinoma without subsequent hysterectomy. However, a woman with stage I endometrial cancer treated at least five years prior to randomization is eligible.
5. Any abnormal uterine bleeding or any endometrial hyperplasia at baseline. Women may become eligible after evaluation and treatment.
6. Abnormal Pap smear. Women with atypical squamous cells of uncertain significance should be evaluated per standard of care, and are eligible. Women with dysplasia of grade CIN-I or greater are ineligible until treated.
7. Uncontrolled diabetes mellitus or hypertension.
8. A myocardial infarction less than 4 weeks prior to randomization.
9. Planned or prior coronary artery bypass grafting.

10. Most recently documented fasting triglycerides >500 mg/dL, \leq four months prior to randomization.
11. Creatinine >2.0 mg/dL.
12. Symptomatic gallstones.
13. NYHA class IV congestive heart failure or known ejection fraction less than 25%.
14. History of hemorrhagic stroke or bleeding diathesis.
15. History of pulmonary embolism, or idiopathic deep venous thrombosis (DVT).
16. History of osteoporosis, unless it is being treated with non-hormonal therapy.
17. Anticipated survival less than three years.
18. Concurrent participation in another masked clinical trial. Participation in an interventional device trial or short term post-PTCA anti-thrombotic trial is permitted so long as follow-up angiography is not part of that trial. If angiography is required, that study's exit angiogram can serve for evaluation as the qualifying angiogram for WAVE.
19. Angiogram not meeting protocol criteria, as judged by the WAVE Central Angiography Laboratory.
20. Unlikely to adhere to the protocol in the opinion of the investigator.

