7.3 RANDOMIZATION

Women who have met all inclusion criteria and have none of the exclusion criteria, and who have signed the informed consent, will be scheduled for a randomization visit. Prior to the randomization visit all women who did not have a blood collection at the screening visit will be advised to fast for at least twelve hours prior to the visit. A blood sample will be collected for central analysis and a local sample for assessment of INR if needed. Data to be collected are indicated in Table 2.

Randomization to one of the four possible study groups (active HRT and placebo antioxidants, active HRT and active antioxidants, placebo HRT and active antioxidants, placebo HRT and placebo antioxidants) will be by a telephone call to the Study Coordinating Center. After confirmation of the patient's eligibility the SCC will issue a

unique patient identifier and medication codes that the clinical center coordinator will use to obtain the woman's study medications. The unique patient identifier will be used on all study forms, laboratory samples, angiograms and any other necessary study documents. Each woman will have a one in four chance of being assigned to each of the four study groups. Randomization will be stratified by clinical center (n=5) and by whether a hysterectomy has been performed. Each woman will be given a seven month supply of her study medications, a medication instruction sheet, a bleeding calendar for those women with a uterus, a bottle of Centrum Silver vitamins (if she requests it), and an appointment for the one month visit.

TABLE 2

WAVE Summary	Screening	Randomization	IM	3M	6M	12M	18M	24M	30M	36M	Exit
Consent	X										
Creat, trig, FSH (if needed)	X										
INR	Obtain at either visit		X								
Study Bloods	Obtain at either visit			X			X			X	
Ht/wt, BP, waist/hip	Obtain at either visit					X		X		X	
Randomization form		X									
Breast, pelvic, Pap, mamm, breast self-exam teaching	X					X		X		X	
Sign medical release	X					X		X		X	
Brachial reactivity	Obtain between consent and initiation of study medication			X							
Dipyridamole SPECT/ETT				X						X	
ECG		X				X				X	
Patient tracking form		X			Update as needed						
Bleeding calendar		X	X	X	X	prn	prn				
Dispense study meds		X			X	X	X	X	X		
Adherence assessment					X	X	X	X	X	X	X
Quality of Life		X		X			X		X		
Follow-up visit*					X	X	X	X	X	X	X
Angiogram	X										X
Physical exam		X				X		X		X	

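### Section 7.2 waives the screening draw on a triglyceride value up to twelve months old, although exclusion 10 uses a four-month window; the one-month INR is also stated inconsistently

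*Protocol*

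**What the plan says.** **Triglycerides.** Exclusion 10 (Section 3.3) reads "Most recently documented fasting triglycerides >500 mg/dL", with the time limit of at most "four months prior to randomization". Section 7.2, which tells the coordinator what to do at screening, says: "If creatinine and fasting triglycerides have been assessed within the past twelve months, no blood collection is necessary at this visit". Blood is drawn for the local laboratory only if those results are not available.

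Two general gates apply. Section 3.1 says "All potential participants with any single exclusion criteria will be excluded", and Section 7.3 schedules for randomization only "Women who have met all inclusion criteria and have none of the exclusion criteria". On blood work at the randomization visit, Section 7.3 says: "A blood sample will be collected for central analysis and a local sample for assessment of INR if needed". Table 2 marks local creatinine, triglycerides and FSH in the screening column alone, and only if needed.

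**One-month INR.** Section 7.4.1 assigns a local INR at this visit to women on Coumadin. Section 8.3 assigns an INR before randomization and at one month to all women. Table 2 marks INR at one month with no restriction, and Section 7.4 points to Table 2 as the summary of what each visit requires.

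**The concern.** The screening instruction and the exclusion it should serve work to different clocks. A coordinator who follows 7.2 can skip the draw on a result that is too old for exclusion 10, and nothing later in the schedule makes good the missing result.

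The exclusion has a safety purpose. Section 2.3.1 says that estrogen raises VLDL-triglycerides, and two of the four study groups receive active HRT. Section 8.4, on HRT side effects, contains no triglyceride check. The later fasting bloods (central study blood at 3 months, triglycerides at 18 months) have no threshold or action attached. The entry exclusion is thus the only triglyceride safeguard with a stated limit and consequence, and women leave the randomization visit with a seven-month drug supply.

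For the INR, the visit instruction is narrower than the safety section it implements. Section 8.3 gives the reason for the test as a possible vitamin E interaction with vitamin K dependent clotting factors. Section 4.2 reports prolonged prothrombin time in vitamin K deficient patients, a group not confined to Coumadin users. A center working from 7.4.1 alone could leave out the test in everyone else.

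**Working it through.** No statistical figure is involved. The check sets the sections side by side, with one subtraction.

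**Step 1: the two triglyceride windows.**

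| Source | Reference date | Maximum age |
|---|---|---|
| Section 7.2 | screening visit | 12 months |
| Section 3.3, exclusion 10 | randomization | 4 months |

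Let L be the months from screening to randomization. A value accepted under 7.2 can be 12 + L months old at randomization, so it can exceed the exclusion 10 window by (12 + L) - 4 = 8 + L months. With L = 0, the smallest case, the excess is 12 - 4 = 8 months. This describes the mismatch; it does not measure impact.

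**Step 2: does any later step supply an in-window result before drug is issued?**

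- Table 2: one local triglyceride entry, at screening, if needed; none at randomization.
- Section 7.3: the local sample at randomization is for INR.
- Section 7.3 and Table 2: a central sample is also taken. Under Section 12.2.8 the central laboratory runs the assays the Steering Committee asks for. No triglyceride result is called for before dispensing.
- Section 7.3: the coordinating center confirms eligibility by telephone before giving medication codes. No laboratory result is named as part of that confirmation.

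So there is one conditional local draw, which 7.2 can switch off, and none after it.

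**Step 3: the consequence under each reading of exclusion 10.**

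- *An in-window value is required.* A center following 7.2 can arrive at randomization without one. The gates in 3.1 and 7.3 still stand, but lack the result they need.
- *Chart-based exclusion only.* A woman is excluded only if a value above 500 mg/dL is on file from the last four months. There is then no literal contradiction. But a value above 500 mg/dL from, say, six months earlier does not exclude her, and under 7.2 it also removes the need for a new draw.

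The mismatch concerns triglycerides only. Exclusion 11 (creatinine) has no time window, so the twelve-month rule does not conflict with it.

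**Step 4: the one-month INR.**

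| Source | Who is tested at one month |
|---|---|
| Section 8.3 | all women |
| Table 2 | unrestricted |
| Section 7.4.1 | women on Coumadin are named; the word only is not used |

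Two places cover everyone and one names a subset. Section 8.3 then treats anticoagulated women separately, as those whose result goes to the private physician, so its coverage of all women looks deliberate.

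**The case against.** **Triglycerides.** Section 7.2 governs when blood must be drawn at one visit; exclusion 10 governs who is kept out. An exclusion keyed to the most recent documented value need not demand a new test, so both can be followed to the letter. A careful site has room to redraw, because Table 2 allows the test if needed and 7.2 does not forbid it. Women who skip the screening draw are told to fast before randomization, so a fasting pre-treatment sample does exist.

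The chart-based reading does remove the literal contradiction. It does not remove the defect, since it leaves an older high value neither excluding nor rechecked. The permissive wording and the eligibility confirmation allow a redraw without scheduling one, while 7.2 tells the coordinator none is necessary. The fasting central sample narrows the gap, but nothing says its result is back before drug is handed out.

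**INR.** Section 8.3 is the dedicated safety section, Table 2 agrees with it, and 7.4.1 does not limit the test in so many words. Harm requires a center to rely on 7.4.1 alone, and women on Coumadin are tested under every reading. All of that stands, and it makes the INR point the smaller of the two. The visit instruction still gives no direction to test anyone else.

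**Conclusion.** The point holds and should be fixed. Section 7.2 accepts triglyceride values at least 8 months older than the window of exclusion 10, and the schedule contains no local triglyceride between that waiver and the issue of drug. Whether this is a direct contradiction or a weak eligibility check depends on how exclusion 10 is read; both readings call for the same correction. The one-month INR is given to all women in two places and to a named subset in a third.

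The scale is modest. The number of women affected cannot be derived from the protocol for either part. Power, type I error and the primary analysis are unaffected. The stake is that centers following 7.2 and 7.4.1 as written would apply a weaker entry check and a narrower safety test than the rest of the protocol intends.

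**What to change.** 1. **Section 7.2.** Waive the triglyceride draw only if a fasting value on file will be no more than four months old on the day of randomization; otherwise draw it at screening. Creatinine can keep the twelve-month rule.
2. **Exclusion 10.** State that a fasting value within that window is required before randomization.
3. **Section 7.4.1.** Assess INR locally in all women at one month, in line with Section 8.3 and Table 2. For women on anticoagulants, send the result to the private physician, as Section 8.3 already provides.

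The cost is three text edits and an occasional extra fasting draw at screening. Sites already track a four-month clock to randomization for the qualifying angiogram (inclusion 2: "Have a WAVE protocol angiogram performed within four months of randomization"). No INR is added beyond those in Table 2.
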